# 7.11.3 Vital Signs

Vital signs measurements include systolic and diastolic blood pressure, pulse, body temperature and respiratory rate. Each vital signs measurement will be summarized using descriptive statistics (N, mean, SD, median, minimum and maximum) for baseline, postdose, and change from baseline to postdose values. Summaries will be presented separately for SRD and MRD by pooled placebo and each TAK-020 dose level.

Individual results for vital sign measurements that meet the Takeda predefined vital signs MAV criteria in Appendix C will be presented in a data listing. If a subject has a MAV for a particular vital sign parameter at a visit, all visits for that subject for that parameter will be listed. The number and percentage of subjects with at least 1 postdose markedly abnormal vital sign

TAK-020-1001	Page 22 of 31
Statistical Analysis Plan Final	22 May 2017

measurement during treatment will be summarized by pooled placebo, each TAK-020 dose level and TAK-020 overall. The mapping of the subjects who meet the MAV criteria will also be created. All postdose observations, including those at unscheduled visits, will be considered to determine if a subject had a MAV during treatment.

All vital sign measurements will be listed by subject in the data listings and markedly abnormal values will be flagged.

Vital signs results for all subjects in the safety analysis set will be summarized separately for the SRD and MRD portions of the study.

# 7.11.4 12-Lead ECGs

Triplicate 12-lead ECGs will be collected at the scheduled 12-lead ECG measurement visits and time points. The average of the triplicate values will be used as analysis endpoint in summaries.

ECG measurements include heart rate, RR interval, PR interval, QRS interval, QT interval, QTcF interval (Fredericia's method) and QTcB interval (Bazett's method). Each ECG measurement will be summarized with descriptive statistics (N, mean, SD, median, minimum and maximum) for baseline, postdose, and change from baseline to postdose values. Summaries will be presented separately for SRD and MRD by pooled placebo and each TAK-020 dose level.

Individual results for 12-lead ECG measurements that meet the Takeda predefined 12-lead ECG MAV criteria in Appendix D will be presented in a data listing. If a subject has a MAV for a particular ECG parameter at a visit, all visits for that subject for that parameter will be listed. The number and percentage of subjects with at least 1 postdose markedly abnormal ECG measurement during treatment will be summarized by pooled placebo, each TAK-020 dose level and TAK-020 overall. If any ECG result in a set of triplicate ECG measurements meets the MAV criteria, the subject will be counted as having a MAV ECG result. The mapping of the subjects who meet the MAV criteria will be also be created. All postdose observations, including those at unscheduled visits, will be considered to determine if a subject had a MAV during treatment

A shift table showing the number of subjects with status changes from baseline to postdose (normal, abnormal not clinically significant and abnormal clinically significant) according to investigator interpretations will be created.

All ECG measurements will be listed by subject in the data listings and markedly abnormal values will be flagged.

ECG results for all subjects in the safety analysis set will be summarized separately for the SRD and MRD portions of the study.

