- 10. Subject has current or recent (within 6 months) gastrointestinal disease that would be expected to influence the absorption of drugs (ie, a history of malabsorption, esophageal reflux, peptic ulcer disease, erosive esophagitis frequent [more than once per week] occurrence of heartburn, or any surgical intervention [eg, cholecystectomy]).
- 11. Subject has a history of cancer, except basal cell carcinoma which has been in remission for at least 5 years prior to Day 1.
- 12. Subject has used nicotine-containing products (including but not limited to cigarettes, pipes, cigars, chewing tobacco, nicotine patch or nicotine gum) within 28 days prior to Check-in Day -1. Cotinine test is positive at Screening or Check-in (Day -1).
- 13. The subject has poor peripheral venous access.
- 14. Subject has donated or lost 450 mL or more of his or her blood volume (including plasmapheresis), or had a transfusion of any blood product within 30 days prior to Day 1.
- 15. Vaccination with any live vaccine within 4 weeks of study drug administration.

TAK-020	
Study No. TAK-020-1001	Page 35 of 101
Protocol Incorporating Amendment No. 4.0	27 March 2017

- 16. Subject has a Screening or Check-in (Day -1) abnormal (clinically significant) ECG. Entry of any subject with an abnormal (not clinically significant) ECG must be approved, and documented by signature by the PI medically qualified subinvestigator.
- 17. Subject has QTcF >450 msec for men and women or PR outside the range of 120 to 220 msec confirmed upon repeat testing within a maximum of 30 minutes, at the Screening Visit or Check-in (Day -1).
- 18. Subject has abnormal Screening or Day -1 laboratory values that suggest a clinically significant underlying disease or subject with the following lab abnormalities:
  - a) ALT or AST  $>1.2 \times$  the ULN.
  - b) Positive screen test for drugs of abuse.
  - c) Positive blood screen for hepatitis B surface antigen (HBsAg), hepatitis C virus (HCV), or human immunodeficiency virus-1 or -2 antibodies.
  - d) A positive test for tuberculosis (TB) (QuantiFERON).

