(h) Pregnancy test (hCG) will be performed for all female subjects.

(j) Triplicate 12-lead ECGs printed in standard format, will be collected at Screening, Check-in (Day -1), Day 1 predose (0 hours) and at 1, 4, 12, 24, 48, 72 and 96 hours postdose or Early Termination.

(k) Telemetry will be performed approximately 2 hours predose until 12 hours postdose on Day 1. Ten (10) sec triplicate ECGs will be extracted at PK time-points for manual reading and precise ECG reading including QT interval measurement.

(l) One blood sample (6 mL) will be collected prior to dosing on Day 1.

(m) Two whole blood samples (2.5 mL per sample) will be collected on Days 1 (predose) and 24 hours postdose.

(n) Blood samples for PK analysis will be collected on Day 1 at predose (within 30 minutes prior to dosing), and at 0.25, 0.5, 0.75, 1, 2, 3, 4, 6, 8, 10, 12, 16, 24, 36, 48, 72, and 96 hours postdose.

(o) Urine samples for PK analysis will be collected on Day 1 at predose (-12-0) and 0-6, 6-12, 12-24, 24-48, 48-72, 72-96 hour postdose intervals.

(p) Blood samples for PD analysis will be collected on Day 1 at predose (within 30 minutes prior to dosing) and at 0.5, 1, 2, 4, 8, 12, 16, 24, 36, 48, 72 and 96 hours postdose.

(q) PTEs will be collected from signing of informed consent up until dosing on Day 1.

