# Appendix C Criteria for Identification of Markedly Abnormal Vital Signs Parameters

Parameter	Lower Criteria	Upper Criteria
Heart rate	<50 beats per minute	>120 beats per minute
PR	≤80 milliseconds	≥200 milliseconds
QT Interval	≤300 milliseconds	≥460 milliseconds
QTcB Interval	≤300 milliseconds	≥500 milliseconds OR
		≥30 milliseconds change from baseline and ≥450 milliseconds
QTcF Interval	≤300 milliseconds	≥500 milliseconds OR
		≥30 milliseconds change from baseline and ≥450 milliseconds
QRS	≤80 milliseconds	≥180 milliseconds

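### The primary ECG markedly-abnormal count cannot separate a PR of 200-220 ms already present at entry from a new one; SAP 7.11.4 should add a count of findings absent before dosing

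*SAP*

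**What the plan says.** - **Entry.** Protocol 7.2, exclusion 17, removes a subject for "PR outside the range of 120 to 220 msec confirmed upon repeat testing". A PR of 200 to 220 ms is therefore eligible. Exclusion 16 adds a documentation step for non-significant abnormalities: "Entry of any subject with an abnormal (not clinically significant) ECG must be approved".
- **MAV limit.** In the SAP's 12-lead ECG criteria table (listed as Appendix D), the upper PR limit is "≥200 milliseconds". It is an absolute limit. The QTcB and QTcF rows differ: below 500 ms, the upper criterion needs a value of at least 450 ms together with "≥30 milliseconds change from baseline".
- **Counting.** SAP 7.11.4 says: "The number and percentage of subjects with at least 1 postdose markedly abnormal ECG measurement during treatment will be summarized". The subject is counted "If any ECG result in a set of triplicate ECG measurements meets the MAV criteria", and unscheduled postdose ECGs are included. Nothing refers to the subject's status before dosing.
- **Status.** Protocol 5.2.1 and SAP 5.1 both make the ECG MAV count one of four primary safety endpoints, defined as meeting the criteria at least once after dosing.
- **Related outputs.** SAP 7.11.4 also plans change-from-baseline summaries of each ECG parameter using triplicate means, a listing of all visits for any flagged parameter, a mapping of flagged subjects, and "A shift table showing the number of subjects with status changes from baseline to postdose", based on the investigator's reading.

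**The concern.** The entry range and the MAV range for PR overlap by 20 ms, both ends included: exactly 200 ms is a MAV, and exactly 220 ms is eligible. A subject who enters in that band and does not change will meet the primary ECG criterion after dosing. The tabulated percentage then mixes findings brought into the trial with findings that arose on treatment.

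This matters most in the dose-level rows. A reader looks there for a dose-related ECG effect, and each row rests on about six subjects. Pooled placebo carries the same background rate, but it cannot show whether the one event in a given row of six is new.

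The SAP already makes this distinction for QTc. Exclusion 17 removes subjects with QTcF above 450 ms, and a QTcF MAV between 450 and 500 ms requires a rise from baseline. PR has no equivalent.

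**Working it through.** **1. Denominators (Protocol 2.0, Number of Subjects; SAP 6.0).** Each cohort has 6 active and 2 placebo subjects.

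- Part 1 (SRD): 9 × 8 = 72, as stated. Active 9 × 6 = 54; placebo 9 × 2 = 18.
- Part 2 (MRD): 7 × 8 = 56, as stated. Active 7 × 6 = 42; placebo 7 × 2 = 14.

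**2. Limits side by side.**

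| Parameter | Allowed at entry | Upper MAV criterion | Can an unchanged eligible subject be a MAV? |
|---|---|---|---|
| PR | 120 to 220 ms | 200 ms or more | Yes, from 200 to 220 ms |
| QTcF | up to 450 ms | 500 ms or more, or 450 ms or more with a rise of 30 ms or more | No |

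At the low end, PR is a MAV at 80 ms or less and entry needs at least 120 ms, so there is no overlap. Exclusion 17 sets no numeric entry limit for the other ECG parameters. Overlap between an entry limit and an MAV limit is therefore shown for upper PR only.

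**3. Effect of one such subject**, at the maximum cohort numbers, as 1/n:

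| Group | SRD | MRD |
|---|---|---|
| One dose level | 1/6 = 16.7% | 1/6 = 16.7% |
| TAK-020 overall | 1/54 = 1.9% | 1/42 = 2.4% |
| Pooled placebo | 1/18 = 5.6% | 1/14 = 7.1% |

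The exact 95% interval for 1/6 is 0.4% to 64.1%. In the added count proposed under the fix, the dose-level entry would be 0/6.

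**4. Prevalence.** The documents give none. Purely as an illustration, if a share p of eligible subjects had PR in the band, the chance of at least one in a dose level of six is 1 − (1 − p)^6. Assumed p of 1%, 2%, 5% and 10% gives 5.9%, 11.4%, 26.5% and 46.9%. The conclusion does not rest on any of these.

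**5. Which readings should define status before dosing?** Triplicates are scheduled at Screening, Day -1 and Day 1 predose, so 3 × 3 = 9 readings. Postdose there are 7 × 3 = 21 in SRD and 8 × 3 = 24 in MRD. Assume independent readings with SD 5 to 10 ms and no drug effect; neither assumption comes from the documents. With q = Φ((200 − μ)/SD), an unchanged SRD subject at true PR μ is wrongly labelled new with probability q^k × (1 − q^21), where k is the number of readings used before dosing.

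| True PR | SD | q | k = 3 | k = 9 |
|---|---|---|---|---|
| 195 ms | 5 | 0.841 | 0.580 | 0.206 |
| 195 ms | 10 | 0.691 | 0.330 | 0.036 |
| 190 ms | 5 | 0.977 | 0.358 | 0.312 |
| 190 ms | 10 | 0.841 | 0.580 | 0.206 |

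At 210 ms the value is at most 0.004. The price of k = 9 is that it excludes more subjects from the added count: at true PR 190 ms, the chance of at least one reading of 200 ms or more before dosing, 1 − q^k, is 0.187 to 0.789 with k = 9, against 0.067 to 0.404 with k = 3. Replicates within a triplicate may well be correlated, so these figures only illustrate the choice of rule. They do not measure the size of the problem.

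**The case against.** The strongest reply is that nothing here is an error. Protocol and SAP define the endpoint identically, 7.11.4 implements it faithfully, and the laboratory and vital-sign MAV tables use the same at-least-once rule. The planned outputs already let a reader resolve a case: with six active subjects per cohort, the all-visit listing puts PR before and after dosing side by side, and the PR change-from-baseline summaries show whether the group moved. Any single event in a group of six gives 16.7%, so that figure is not peculiar to PR. The proposed count leaves the primary percentage as it is and will itself misclassify some borderline subjects.

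Most of this stands, and it limits the point to an improvement in presentation. It does not remove the point. The listing and mapping work one subject at a time. The shift table follows investigator interpretation and not MAV status. The change summaries use triplicate means, while the MAV rule uses single readings. None of these outputs gives the number of subjects with a MAV that was absent before dosing.

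A reader might infer that the primary ECG endpoint is invalid, or that the comparison with placebo is biased. The documents do not support that. Allocation is randomized, placebo is pooled within each part, and the background rate is common to both arms, so the contrast is at most slightly diluted. Nor does the point reach dose escalation through the listed limits: PR is not among the dose-limiting toxicities in Protocol Table 6.a or the criteria in Protocol 6.1.2.

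**Conclusion.** The point holds as a gap in presentation with a cheap remedy, of low to moderate priority. As written, the primary ECG MAV count would include an eligible subject whose PR of 200-220 ms never changed. Such a subject would appear as 1/6 = 16.7% of a full dose level, 1.9% (SRD) or 2.4% (MRD) of TAK-020 overall, or 5.6% or 7.1% of pooled placebo. These figures assume full cohorts, the maximum number of cohorts and exactly one such subject; a repeated dose level or a missing subject changes the denominator.

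The documents do not show that such a subject was enrolled and give no prevalence, so no expected number of affected dose levels can be stated. The endpoint is descriptive and the sample size was not based on power, so no formal test is affected.

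**What to change.** In SAP 7.11.4, keep the protocol-defined ECG MAV count unchanged. Beside it, by pooled placebo, each TAK-020 dose level and TAK-020 overall, add the number and percentage of subjects who met the criterion for a parameter at any postdose reading but at no reading before the first dose. Specify:

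- **Denominator:** all treated subjects in the group, as for the protocol-defined count (for example 0/6, not 0/5), so that the two columns compare directly.
- **Status before dosing:** the same any-replicate rule, over all ECGs before the first dose, scheduled (Screening, Day -1, Day 1 predose) and unscheduled, to match the postdose rule. Say before the first dose explicitly, because the Part 2 schedule also labels ECGs on Days 3, 5, 9 and 10 as predose.
- **QTc rows:** only the absolute limits before dosing, since a change from baseline has no meaning there.

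The cost is SAP wording and one added column or row. No new data are needed, and the protocol endpoint does not change. There are two downsides. A subject already over the limit who worsens (say from 205 to 260 ms) appears only in the protocol-defined count and the listing. Some borderline subjects will be misclassified in either direction. Both counts must therefore be shown together.

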# 7.11.5 Other Observations Related to Safety

Cardiac monitoring telemetry will be performed at different scheduled times from approximately 2 hours predose until 12 hours postdose on Day 1 for SRD and both Day 1 and Day 9 for MRD. Ten second triplicate ECG parameters will be summarized using descriptive statistics for

TAK-020-1001	Page 23 of 31
Statistical Analysis Plan Final	22 May 2017

baseline, postdose and change from baseline to postdose using the average of the triplicate values. All cardiac monitoring telemetry results will be listed by subject in the data listings and markedly abnormal values will be flagged.

Liver function test results will be presented in the data listings. No summary tables will be provided.

Physical examination findings will be presented in the data listings. No summary tables will be provided.

Pharmacogenomic sample collection data will be presented in the data listings. No summary tables will be provided.

#### 7.12 Interim Analysis

Not applicable.

# 7.13 Changes in the Statistical Analysis Plan

Not applicable.

# Appendix A Schedule of Study Procedures Part 1 (SRD)

	Screening	Check-in	Treatment		Check-out	Early Termination	Follow-up		
	Days -28		Day	Day	Day	Day			Day 14
Study Day:	to -2	Day -1	1	2	3	4	Day 5	(a)	(±2) (b)
Confinement		Х	X	X	X	X	Х		
Informed consent	Х								
Inclusion/exclusion criteria	Х	Х							
Demographics and medical history	Х	Х							
Medication history	Х								
Physical examination	Х		X(c)	X	Х	Х	Х	Х	
Vital signs (d)	Х	Х	X	X	Х	Х	Х	Х	
Weight, height, and BMI (e)	Х	Х					Х	X	
Concurrent medical conditions	Х	Х							
Concomitant medications (f)	Х	Х	X	X	Х	Х	Х	X	Х
Clinical laboratory tests (g)	Х	Х		X	Х		Х	Х	
Hepatitis panel	Х								
HIV screening	Х								
TB screening	Х								
Pregnancy test (hCG) (h)	Х	Х					Х	Х	
Urine drug/alcohol/cotinine screen	Х	Х							
ECG (j)	Х	X	X	X	X	X	Х	X	
Telemetry (k)			X						
PGx DNA sample collection (l)			X						
PGx RNA sample collection (m)			X	X					
PK blood collection (n)			X	X	Х	Х	Х	Х	
PK urine collection (o)			X	X	Х	Х	Х	Х	
CCI									
CCI									
Dispense study medication			X						
PTE assessment (q)	Х	Х	X						
AE assessment			X	X	Х	Х	Х	Х	Х

Footnotes are on the next page.

TAK-020-1001			
Statistical Analysis	Plan	Final	

(a) Conduct procedures for subjects discontinued early. The PK sample collection should be collected at the Early Termination Visit, if possible. For example, collect samples if early withdrawal is due to an AE, and/or if several hours elapsed since last blood draw.

(b) The Follow-up Visit will occur by telephone on Day 14 ( $\pm 2$ ) unless abnormal, clinically significant findings were observed upon discharge. In these cases, subjects must then be brought back to the clinic for re-evaluation per investigator's discretion. (c) The physical examination can be conducted within 24 hours prior to study drug administration.

(d) Vital signs (oral temperature, sitting pulse, and blood pressure) will be collected at Screening and Check-in (Day -1), Day 1 predose (0 hours) and at 1, 4, 12, 24, 48, 72, 96 hours postdose or Early Termination.

(e) Height will only be collected at Screening.

(f) Record all medications (other than study drug) from Screening and throughout the study.

(g) Clinical laboratory tests (hematology, serum chemistries, and urinalysis) will be collected at Screening, Day -1, Days 2 and 3, and prior to check-out (Day 5) or Early Termination. Laboratory samples will be taken following a minimum 10-hour overnight fast.

(h) Pregnancy test (hCG) will be performed for all female subjects.

(j) Triplicate 12-lead ECGs printed in standard format, will be collected at Screening, Check-in (Day -1), Day 1 predose (0 hours) and at 1, 4, 12, 24, 48, 72 and 96 hours postdose or Early Termination.

(k) Telemetry will be performed approximately 2 hours predose until 12 hours postdose on Day 1. Ten (10) sec triplicate ECGs will be extracted at PK time-points for manual reading and precise ECG reading including QT interval measurement.

(l) One blood sample (6 mL) will be collected prior to dosing on Day 1.

(m) Two whole blood samples (2.5 mL per sample) will be collected on Days 1 (predose) and 24 hours postdose.

(n) Blood samples for PK analysis will be collected on Day 1 at predose (within 30 minutes prior to dosing), and at 0.25, 0.5, 0.75, 1, 2, 3, 4, 6, 8, 10, 12, 16, 24, 36, 48, 72, and 96 hours postdose.

(o) Urine samples for PK analysis will be collected on Day 1 at predose (-12-0) and 0-6, 6-12, 12-24, 24-48, 48-72, 72-96 hour postdose intervals.

(p) Blood samples for PD analysis will be collected on Day 1 at predose (within 30 minutes prior to dosing) and at 0.5, 1, 2, 4, 8, 12, 16, 24, 36, 48, 72 and 96 hours postdose.

(q) PTEs will be collected from signing of informed consent up until dosing on Day 1.

# Part 2 (MRD)

	Screening	Check-in	Treatment	Washout	Treatment	Check-out	Early Termination	Follow-up Visit
	Dave -28	CIICCK-III	Treatment	washout	Treatment	Check-out	Termination	Day 17
Study Day:	to -2	Day -1	Day 1	Day 2	Day 3-9	Day 10	(a)	$(\pm 2)$ (b)
Confinement		Х	Х	Х	X	Х		
Informed consent	Х							
Inclusion/exclusion	Х	X						
criteria								
Demographics and medical history	Х	X						
Medication history	Х							
Physical examination	Х		X (c)	Х	Х	Х	Х	
Vital signs (d)	Х	Х	Х	Х	Х	Х	Х	Х
Weight, height, and BMI (e)	Х	X				Х	Х	
Concurrent medical conditions	Х	X						
Concomitant medications (f)	Х	X	Х	Х	X	Х	X	Х
Clinical laboratory tests (g)	Х	X		X	X	X	Х	X (s)
Hepatitis panel	Х							
HIV screening	X							
TB screening	X							
Pregnancy test (hCG) (h)	Х	X				X	X	
Urine drug/alcohol/cotinine screen	Х	X						
ECG (i)	Х	Х	Х	Х	Х	Х	Х	
Telemetry (j)			Х		X			
PGx DNA sample collection (k)			Х					
PGx RNA sample collection (l)			Х		X			
PK blood collection (m)			Х	Х	X	Х	Х	
PK urine collection (n)			X	Х	X	Х	Х	
CCI			1		1	1		
CCI								
Dispense study medication			X		X			
PTE assessment (r)	Х	X	Х					
AE assessment			Х	Х	X	Х	X	Х

Footnotes are on the next page.

TAK-020-1001	Page 28 of 31
Statistical Analysis Plan Final	22 May 2017

(a) Conduct procedures for subjects discontinued early. The PK sample collection should be collected at the Early Termination Visit, if possible. For example, collect samples if early withdrawal is due to an AE, and/or if several hours elapsed since last blood draw].

(b) All subjects will return to the unit and complete Hematology and Serum Chemistry tests, vital signs, concomitant medications, and AE assessment.

(c) The physical examination can be conducted within 24 hours prior to study drug administration.

(d) Vital signs (oral temperature, sitting pulse, and blood pressure) will be collected at Screening and Check-in (Day -1) and on Day 1 at predose (0 hours) and 1, 4, 12, 24 hours postdose, then twice daily until Study Exit (Day 10) or Early Termination and once during the Follow-up visit.

(e) Height will only be collected at Screening.

(f) Record all medications (other than study drug) from Screening and throughout the study.

(g) Clinical laboratory tests (hematology, serum chemistries, and urinalysis) will be collected at Screening, Day -1, Days 2, 3, 5, 8 and prior to check-out (Day 10) or Early Termination. Laboratory samples will be taken following a minimum 10-hour overnight fast

(h) Pregnancy test (hCG) will be performed for all female subjects.

(i) Triplicate 12-lead ECGs printed in standard format, will be collected at Screening, Check-in (Day -1), Day 1 predose (0 hours) and at 1, 4, 12, and 24 hours postdose, Days 3, 5, 9, 10 at predose (0 hours) or Early Termination.

(j) Telemetry will be performed approximately 2 hours predose until 12 hours postdose on Days 1 and 9 only. Ten (10) sec triplicate ECGs will be extracted at PK time-points for manual reading and precise ECG reading including QT interval measurement.

(k) One blood sample (6 mL) will be collected prior to dosing on Day 1.

(I) Two whole blood samples (2.5 mL per sample) will be collected at predose on Days 1, 3 and 9.

(m) Blood samples for PK analysis will be collected at predose on Day 1 (within 30 minutes prior to dosing) and at 0.25, 0.5,

0.75, 1, 2, 3, 4, 6, 8, 10, 12, 16, 24, 36, and 48 hours postdose and at predose on Day 9 (within 30 minutes prior to dosing) and at 0.25, 0.5, 0.75, 1, 2, 3, 4, 6, 8, 10, 12, 16, and 24 hours postdose.

(n) Urine samples for PK analysis will be collected on Day 1 and Day 9 at predose (-12-0), and 0-6, 6-12, 12-24 hour postdose intervals.

(r) PTEs will be collected from signing of informed consent up until dosing on Day 1

(s) Hematology and Serum Chemistry only.

TAK-020-1001	Page 29 of 31
Statistical Analysis Plan Final	22 May 2017

